1.3 Problem statement

Defining the optimum dosing strategy for a population, subgroup, or individual patient requires resolution of the variability issues. Pharmacologic measures of drug exposure are critical to the interpretation of results of PrEP studies and implementation programs. Benchmark concentrations for TFV-DP in DBS and, PBMCs with DOT dosing have been established for US individuals. Because many antiretroviral drugs including TDF-based PrEP may exhibit variable pharmacokinetics due either demographics, genetic variation in drug transporter physiological changes in pregnancy, or pathological changes, context-specific studies are needed. No controlled studies have been conducted in African cisgender women including pregnant cisgender women.

1.4 Justification

African cisgender women, particularly those ≤ 24 years, face disproportionate HIV risk, accounting for more than half of new infections on that continent, and with incidence rates that are often double or more than their male age-mates. Thus, African cisgender women at risk for HIV are a priority group for HIV prevention, including PrEP, but variable adherence in PrEP clinical trials and limited pharmacologic data have resulted in lack of clarity about the degree of PrEP use required for HIV protection. For MSM, the STRAND and DOT-DBS studies of DOT of TDF/FTC PrEP defined blood TFV-DP concentrations arising from 2, 4, and 7 DOT doses per week. When STRAND data were applied to the iPrEx trial cohort they helped define robust adherence-efficacy thresholds for MSM. Those thresholds are today being applied to studies of African cisgender women taking PrEP, and cisgender women-specific HIV protective levels have never been defined. However, recent data from large PrEP studies we have done among African cisgender women suggest those STRAND levels may not reflect the pharmacology of cisgender women in African settings, in general and particularly in pregnancy when TFV-DP concentrations may be 45%-58% lower. Single-dose tissue pharmacology studies suggest oral TDF/FTC PrEP dosing delivers 20- to 100-fold higher TFV-DP in rectal tissue compared with vaginal tissue, suggesting cisgender women may need extraordinary perfection for HIV protection; on the other hand, in clinical studies in cisgender women with reasonable-but-imperfect PrEP adherence, suggest important levels of HIV protection. Furthermore, pregnant cisgender women have been excluded from many early studies of novel therapeutics, including PrEP, resulting in delays for pregnant cisgender women to gain access to PrEP and benefit from normative recommendations about the safety of PrEP in pregnancy and breastfeeding^{64, 65}. Recent data from the IMPAACT 2009 study of DOT PrEP in pregnant and postpartum cisgender women showed that DBS TFV-DP concentrations were 30-40% lower in pregnant vs postpartum cisgender women⁵⁶. However, this study did not assess concentrations in PBMCs which are relevant to address the critical question of whether the observed reductions are of clinical significance. Thus, there is need to understand blood concentrations of PrEP medications and their relationship to HIV protection in non-pregnant and pregnant cisgender women. A DOT study of PrEP in cisgender women to define adherence-concentration thresholds is overdue and completely necessary for the field.

2 STUDY OBJECTIVE AND DESIGN

2.1 Overall Hypothesis

TDF/FTC dose-response thresholds from DOT PrEP dosing for cisgender women will be defined but will differ from thresholds defined for MSM populations; pregnant cisgender women will have lower benchmark concentrations in PBMC.

2.2 Overall Objective

The central objective of this proposal is to describe blood and tissue adherence-concentration benchmarks for DOT TDF/FTC PrEP for Kenyan cisgender women and quantify the impact of pregnancy on benchmark thresholds.

2.3 Primary Objectives

- 1) To define the cisgender women-specific expected blood concentrations and dose-proportionality for TFV-DP in DBS and PBMCs in cisgender women using directly observed TDF/FTC therapy at 2, 4, 7 doses per week.
- 2) To establish a model to predict adherence rate to TDF/FTC by level of TFV-DP in DBS for cisgender women.

2.4 Secondary Objectives

- 1) To define the expected concentrations and dose-proportionality for TFV-DP in PBMC and vaginal tissue
- 2) To quantify the effect of pregnancy on the benchmark concentrations of TFV, TFV-DP, FTC, and FTC-TP in pregnant cisgender women using daily DOT FTC-TDF PrEP
- 3) Examine relationships among drug concentrations in plasma, WB, DBS, and PBMC.
- 4) To determine the influence of biological variables (e.g. mean corpuscular volume and HCT, age, weight, sex, metabolites from metabolomics, and genetic variability in drug transporter/clearance proteins) on drug concentrations.
- 5) Compare drug concentrations in DBS from fingerstick versus transferring blood from blood tubes.

[figure not shown]
2.5 Study Design

We will implement two distinct but complementary study designs: 1) An open-label, randomized, three-arm, directly observed therapy, pharmacologic study among low-risk HIV-uninfected non-pregnant cisgender women, and 2) A contemporaneous cohort of pregnant cisgender women at high risk for HIV to receive daily directly observed therapy PrEP dosing.

2.5.1 Study design for non-pregnant cisgender women

This is an open-label, randomized, three-arm, directly observed therapy, pharmacologic study. HIV-uninfected non-pregnant cisgender women at low risk for HIV will be randomly assigned to 1 of 3 dosing frequencies of DOT TDF/FTC PrEP (**Figure 4**): 2, 4, or 7 doses per week to help differentiate poor and modest from perfect dosing (**Figure 4**).

Figure 4: Schema for directly observed TDF/FTC PrEP dosing and pharmacologic sampling

Enrollment will continue until 54 for non-pregnant evaluable participants (i.e., participant with completed data on dosing and PK samples) are enrolled.

- **Group #1:** “7 doses per week or Perfect Adherence arm”— cisgender women will receive a single tablet of co-formulated 300 mg TDF/ 200mg FTC once daily (7 doses per week).
- **Group #2:** “4 doses per week or Moderate Adherence arm” — cisgender women will receive a single tablet of co-formulated 300 mg TDF/ 200mg FTC tablet on Monday, Tuesday, Thursday, Friday.
- **Group #3:** “2 doses per week or Poor Adherence arm” — cisgender women will receive a single tablet of co-formulated 300 mg TDF/ 200mg FTC tablet on Monday and Tuesday.

Justification for non-daily dosing of PrEP groups:

In this study we propose to randomize cisgender women (non-pregnant cohort) to non-daily dosing of PrEP (2, or 4 doses per week). The non-daily dosing is needed to help investigate and demonstrate dose proportionality of TFV and TFV-DP concentrations. The adherence-concentration thresholds derived from this dosing frequency will help guide clinical decisions on drug levels associated with HIV protection in cisgender women and adherence level required to achieve those concentrations. Only daily PrEP is recommended by WHO and the Kenya national guidelines for protection from vaginal HIV exposure and we have carefully considered the risks associated with non-daily in planning this proposal. As detailed in eligibility section, only non-pregnant cisgender women at low HIV risk based on Kenya guidelines will be enrolled and cisgender women will receive full package of HIV prevention, including risk reduction counseling, condoms and STI treatment at each visit. We will also perform monthly HIV testing.

2.5.2 Study design for pregnant cisgender women

This will be an open-label, non-randomized, single-arm, pharmacologic study of daily directly observed therapy. In addition to the cohort of non-pregnant cisgender women describe above, a contemporaneous cohort of up to 18 pregnant cisgender women will be recruited to evaluate the impact of pregnancy on blood and cellular drug benchmark concentrations. Cisgender women must be at 13-26 weeks gestation to give sufficient time for 8 weeks of DOT follow-up. This gestation age was chosen to balance feasibility and risk-benefit and is informed by preliminary work we have done that shows greater reduction in TFV and TFV-DP concentrations in the 2nd and 3rd trimester’s compared to the 1st trimester⁵². We will make all effort to have cisgender women across the entirety of this gestation age spectrum to allow analyses that look across the 2nd and 3rd trimester. To ensure an ethical approach for provision of PrEP in pregnancy (i.e., only exposing PrEP to those who want and might benefit from it) all pregnant cisgender women will be at high risk for HIV and willing to use PrEP. HIV risk and eligibility will be determined according to the Kenya guidelines for PrEP, as described in Table 3. Pregnant cisgender women will receive only daily PrEP dosing (7 doses per week) and matched on age to non-pregnant cisgender women in daily dosing arm. After 8 weeks of DOT PrEP, pregnant cisgender women will be linked to continue PrEP at the clinic of their choice, including at the Thika site clinic itself, permitting seamless access to PrEP and continuation after the study.

Table 3: Kenya national guideline indicators of substantial risk for HIV and indication for PrEP:

Partner of HIV-infected person not on ART or on ART for <6 months
Has >1 partner of unknown status
Engages in transactional sex
History recent STI (past 6 months)
Recurrent PEP use
Inconsistent or no condom use
Injection drug use.

2.6 Enrollment Targets

A cohort of up to 72 cisgender women who meet the inclusion and exclusion criteria described in Section 3 below will be enrolled at the KEMRI Thika Research Site, in Thika, Kenya. The target enrollment is to have at least 60 evaluable participants (both pregnant and non-pregnant) at the end of the study (i.e. have complete set of all protocol pharmacological samples). As described in Section 3.8, women with incomplete set of pharmacological samples will be replaced but no more 20% or up to 72 total cisgender women who agree to enroll. i.e., 54 low risk non-pregnant cisgender women and 18 pregnant cisgender

women at elevated risk of HIV. The cohort of 54 cisgender women who accept PrEP will be randomized 1:1:1: **2, 4, or 7** DOT doses per week to help differentiate poor and modest from perfect dosing. Pregnant cisgender women will receive only daily DOT dosing.

3 STUDY POPULATION

We will enroll a novel cohort of up to 54 healthy, HIV-uninfected non-pregnant Kenyan cisgender women volunteers 18-30 years to establish benchmark adherence-concentration thresholds for TDF-based PrEP, plus a contemporaneous cohort of up to 18 pregnant Kenyan cisgender women at elevated HIV risk to quantify the impact of pregnancy periods on benchmark adherence-concentration thresholds. Participants will be selected for the study according to the criteria in Sections 3.1 and 3.2. They will be recruited, screened, and enrolled as described in Section 3.3. Issues related to participant retention and withdrawal from the study are described in Sections 3.5 and 3.6, respectively.

3.1 Inclusion Criteria

This study will enroll young Kenyan cisgender women (aged 18-30 years old). Cisgender women bear the greatest burden for HIV infection; thus, the study will focus solely on cisgender women. HIV incidence is greatest in younger cisgender women, as is PrEP interest in accumulating data from Kenya, and the age limitation reflects that clinical and epidemiologic need. Enrollment criteria will be finalized at the time of protocol development to account for any updates to Kenyan national guidelines, but the central clinical criteria are as follows:

For all cisgender women

- Age ≥ 18 and ≤ 30 years old
- Willing to undergo urine pregnancy tests
- Has understood the information provided and has provided written informed consent before any study-related procedures are performed.
- HIV uninfected based on negative HIV rapid tests, according to Kenyan national algorithm
- Normal renal function (estimated glomerular filtration rate >60 mL/min)
- Hepatitis B surface Ag negative
- No active clinically significant medical or psychiatric conditions that would interfere with study participation
- Lack of severe anemia
- Willing to use DOT and come to clinic frequently for DOT PrEP for at least 8 weeks
- Willing to have home visits for follow up
- Has an active smartphone to allow off-site observation of dosing
- Intention to stay within the study site's catchment area for at least 8 weeks.
- Resides or works in catchment area with high speed internet coverage to permit video streaming

Specific for non-pregnant cisgender women cohort

- Not pregnant or breast feeding
- At low risk for HIV. *In Kenya, national guidelines define substantial risk for HIV and recommend PrEP be an option for individuals reporting: partner of HIV-infected person not on ART or on ART for <6 months, >1 partner of unknown status, transactional sex, recent STI, recurrent PEP use, inconsistent condom use, or injection drug use. So, non-pregnant cisgender women reporting any of these factors will not be eligible for the study but will be linked for PrEP at clinic of choice including at Thika Site itself.*
- Willing to be randomized to non-daily PrEP and come to clinic frequently for DOT PrEP
- Willingness and ability to be abstinent for at least 7 days after each vaginal biopsy visit.

Specific for pregnant cisgender women only

- At screening, evidence of a viable pregnancy with gestational age of 13-26 weeks after the date of conception with sonographic confirmation. *If adequate sonographic results are not available from medical records at screening, an ultrasound must be performed in the interim so that the result is available at study entry.*
- At elevated risk for acquiring HIV according to Kenya guideline for PrEP. This is to ensure an ethical approach for provision of PrEP in pregnancy (i.e., only exposing PrEP to those who want and might benefit from it). *Kenya national guidelines define substantial risk for HIV and recommend PrEP be an option for individuals reporting partner of HIV-infected person not on ART or on ART for <6 months, >1 partner of unknown status, transactional sex, recent STI, recurrent PEP use, no or inconsistent condom use*
- At study entry, willing to use PrEP during pregnancy for HIV prevention

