3.2 Exclusion Criteria

For all cisgender women

- Inability to give informed consent
- Positive screening HIV+ as determined by standard rapid serologic assays or suspected acute HIV infection in the opinion of the clinician. (example signs and symptoms of acute HIV infection include combinations of fever, headache, fatigue, arthralgia, vomiting, myalgia, diarrhea, pharyngitis, rash, night sweats, and adenopathy cervical or inguinal)
- Positive HBV surface antigen test at screening
- Calculated creatinine clearance < 60 ml/min.
- Any laboratory value or uncontrolled medical conditions that, in the opinion of the investigators, would interfere with the study conditions such as, heart disease and/or cancer.
- Prohibited concomitant medications are: investigational agents (within 30 days of enrollment), aminoglycosides, ganciclovir/valganciclovir, chronic high-dose acyclovir/valacyclovir (>800mg acyclovir or > 500mg valacyclovir for >7 days), cyclosporine, amphotericin B, foscarnet, and cidofovir, and products with same or similar active ingredients as the study medications including TAF®, ATRIPLA®, COMPLERA®, EMTRIVA®, VIREAD®; or drugs containing lamivudine or adefovir, which are close analogs of FTC and tenofovir, respectively.
- Current or past use of PrEP (pre-exposure prophylaxis)
- Not willing to have home visits

Specific for non-pregnant cisgender women cohort

- Pregnancy or plan to become pregnant in the next 6 months or unwillingness to use birth control
- Current breastfeeding
- High risk of HIV infection (for example: sexually active with an HIV infected partner; engages in condomless intercourse with HIV-infected partners or partner of unknown status during the study; females who exchange sex for money, shelter, or gifts; active injection drug use or during the last 12 months; newly diagnosed sexually transmitted infections in last 6 months.

Specific for pregnant cisgender women cohort

- Mother has a known history of any of the following, as determined by the site investigator or designee based on maternal report and available medical records:
- Sick cell anemia (excluding sick cell trait), chronic bleeding, blood transfusion within the past 120 days (excluding for chronic illness) or other blood dyscrasias
- Fetus has a known or suspected major congenital anomaly, from chart review of prior data, defined ultrasound.
- Complications in prior pregnancies that would be considered exclusionary

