5.2.1 Dosing schedule and assessment of compliance

The design of the study is guided by the ~17 day half-life of TFV-DP in DBS, including 8 weeks of dosing to achieve approximately 90% of steady-state, weekly sampling at convenience times (i.e., rather than troughs), and three dosing groups (2, 4, and 7 doses per week) to demonstrate dose-proportionality. All cisgender women will be followed for 8 weeks with DOT PrEP to establish steady state in DBS and WB, and up to 8 weeks for two post-DOT PrEP sampling visits. We have chosen a dosing frequency scheme for non-daily doses to directly replicate the STRAND DOT study schedule based on the ~17 day half-life of TFV-DP in DBS: The 2 doses per week will be taken on Monday and Tuesday, and the 4 doses per week on Monday, Tuesday, Thursday, and Friday. This schedule will permit simultaneous evaluation of concentrations derived from intermittent and day-by-day dosing. The operationalization of specific days for dose taking can be adjusted prior to study start while maintaining the randomized adherence patterns (frequency of dosing taking) to permit efficient study operations and to minimize the burden on study participants. This is possible due to TFV-DP long half-life and planned sampling at steady state. Therefore, any chosen days would still be appropriate.

All doses will be witnessed, as described above, in person by a study personnel in private room at the Thika clinic or other predetermined location to maximize convenience for the participant. On dosing visits, the participant will take the dose by mouth and study personnel will ensure the tablet is swallowed by

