5.2.2 Protocol pharmacology sampling visit schedule

On protocol-specified clinic visits (described below and Table 5), a blood sample will be collected from an arm vein for plasma/WB/RBC/DBS/PBMC isolation and safety laboratories. Hair will be cut from the scalp for comparison with other drug measures. Adverse events will be assessed. All protocol-specified clinic visits are detailed below. Each protocol-specified clinic visit will have a window of up to three days for sample collection (up to a week for hair).

Clinic visit 1: Study entry visit (must be within 30 days after screening visit)

- Medical, sexual, contraception, antenatal and vaccine history review
- Obtain study blood work: WB, DBS, PBMC, plasma, (pre-drug for endogenous molecules such as nucleosides)
- Urine β HCG
- Study urine: (baseline endogenous molecules such as nucleosides)
- STI tests (CT, GT, syphilis)
- hDNA
- Vaginal swab
- Dispense back up PrEP medication: subject home supply
- Dispense study dosing calendar
- DOT: Witness first PrEP dose

Clinic visit 2: Week 1 Dose 4 visit (for 2 doses per week group this will be 4 days since first dose:

- Study Bloodwork: WB, DBS, PBMC, plasma
- Study urine
- Finger stick for DBS
- Cervicovaginal biopsy: Random **subset (50%) of non-pregnant cohort only**
- Vaginal swab
- Medical, sexual, contraception, antenatal and vaccine history review
- AE assessment
- Concomitant Medication Review
- DOT

Clinic visit 3: Week 1 (Dose 7) visit:

- Study bloodwork: WB, DBS, PBMC, plasma
- Study urine
- Finger stick for DBS
- Vaginal biopsy: **Random subject (50%) of non-pregnant cohort only**
- Vaginal swab
- Blood work: hDNA for those who consent to drug transport gene testing.
- Medical, sexual, contraception, antenatal and vaccine history review
- AE assessment
- Concomitant Medication Review
- DOT

Clinic visit 4: Week 2 (Dose 14) visit:

- Study bloodwork: WB, DBS, PBMC, plasma
- Study urine
- Medical, sexual, contraception, antenatal and vaccine history review
- AE assessment
- Concomitant Medication Review
- DOT

Clinic visit 5: Week 3 (Dose 21) visit:

- Study bloodwork: WB, DBS, PBMC, plasma
- Study urine
- Medical, sexual, contraception, antenatal and vaccine history review
- AE assessment
- Concomitant Medication Review
- DOT

Clinic visit 6: Week 4 (Dose 28) visit:

- HIV rapid test
- Urine β HCG
- Study bloodwork: WB, DBS, PBMC, plasma
- Study urine
- Vaginal biopsy: **Non-pregnant cohort only**
- Vaginal swab
- Hair collection

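### Recently completed PEP is an unguarded route into the pregnant cohort, and the planned first-order curve has no term for TFV-DP already present at the first dose

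*Combined protocol and SAP*

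**What the plan says.** **Eligibility.** For the pregnant cohort, Section 3.1 (and Table 3 in Section 2.5.2) lists alternative qualifying risk factors, including "transactional sex, recent STI, recurrent PEP use, no or inconsistent condom use". No recency limit is put on PEP. For the other cohort the same list works in reverse: "non-pregnant cisgender women reporting any of these factors will not be eligible for the study".

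**Prior drug.** Section 3.2 excludes everyone with "Current or past use of PrEP (pre-exposure prophylaxis", at any time, but does not mention PEP. The bar on "products with same or similar active ingredients as the study medications including" several named brands, and on lamivudine, sits in the list of prohibited concomitant medications and has no look-back. The one washout in that list belongs to "investigational agents (within 30 days of enrollment".

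**Entry sample.** Visit 1 in Section 5.2.2 draws whole blood, DBS, PBMC and plasma, described as "pre-drug for endogenous molecules such as nucleosides". Section 9.1 confirms that this draw precedes the first dose. No section says that TFV-DP will be measured in it, or what follows if it is quantifiable.

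**Analysis.** Section 7.3.1 uses week 8 values as measured for dose proportionality. It also fits C_t = Css × (1 − e^(−kt)) and feeds the fitted Css into the same model. Section 7.3.2 (item 2) describes the pregnancy comparison only as modelling, stratified by age and gestation, with no term for earlier drug.

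**The concern.** Excluding any past PrEP suggests that the study wants women with no earlier exposure. PEP is the obvious other source of such exposure, and in one cohort its repeated use is a way in. Carry-over from recurrent PEP would therefore fall on the pregnant side of the pregnancy comparison (secondary objective 2) and not on the other.

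The marker is slow: "The design of the study is guided by the ~17 day half-life of TFV-DP in DBS". Drug from a course that ended weeks earlier would still be measurable, and a curve that must pass through zero has nowhere to put it except in k and Css. At stake are the early concentrations, the fitted half-life and plateau and, to a small degree, the estimated effect of pregnancy.

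**Working it through.** **Inputs from the protocol.** DBS half-life 17 days (Section 5.2.1); 8 weeks of dosing; pregnant-cohort bloods at weeks 0, 1, 2, 4, 6, 8 and 9 (Table 5 footnote); up to 18 pregnant women (Section 2.5.2); expected reduction in pregnancy of 30–40% or 45–58% (Section 1.4).

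**Assumptions not in the protocol.** PEP contains tenofovir, is taken daily for 28 days, and has the same kinetics as the study drug. The gap between last PEP dose and entry is varied.

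**The plan's own figure.** 56/17 = 3.29 half-lives, and 1 − 2^(−56/17) = 0.898. This agrees with the stated 90% of steady state at week 8. Also 0.9 × 1605 = 1444.5, the stated 1445.

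**Starting level.** For a gap of g days, C0/Css = (1 − 2^(−28/17)) × 2^(−g/17) = 0.681 × 2^(−g/17). At g = 14: 0.681 × 0.565 = 0.38. At g = 30: 0.681 × 0.294 = 0.20.

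**Inflation of her own concentration at day t.** (C0/Css) × 2^(−t/17) / (1 − 2^(−t/17)). For g = 14 at week 1: 0.385 × 0.752 / 0.248 = 1.16, or 116%. At week 8: 0.385 × 0.102 / 0.898 = 0.044, or 4.4%.

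**Zero-start fit.** The true profile is Css × (1 − e^(−kt)) + C0 × e^(−kt), with Css = 1 and half-life 17 days. The planned curve was fitted to it by least squares, without noise, at weeks 1, 2, 4, 6 and 8.

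| Gap (days) | C0/Css | Week 1 | Week 4 | Week 8 | Fitted Css | Fitted half-life (days) |
|---|---|---|---|---|---|---|
| 0 | 68% | +206% | +32% | +7.7% | 0.92 | 3.1 |
| 14 | 38% | +116% | +18% | +4.4% | 0.89 | 6.4 |
| 30 | 20% | +61% | +9% | +2.3% | 0.91 | 10.0 |
| 60 | 5.9% | +18% | +2.8% | +0.7% | 0.96 | 14.4 |
| 90 | 1.7% | +5% | +0.8% | +0.2% | 0.99 | 16.2 |

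Section 9.1 describes day 4 and weekly sampling for each group. On that fuller schedule the fit gives 0.869 and 5.2 days (14-day gap) or 0.895 and 9.4 days (30-day gap), so the conclusion does not depend on which schedule is followed.

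The two approaches err in opposite directions. Measured values go up, which makes the pregnancy reduction look smaller. Fitted Css goes down, because raised early points make the curve level off too soon, and this makes the reduction look larger.

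**Cohort effect at week 8.** If 3 of 18 women came straight from PEP, the geometric mean rises by 1.077^(3/18) − 1 = 1.3%, and a true pregnant to non-pregnant ratio of 0.65 would read 0.658. With 6 of 18 it rises by 2.5% (0.666). If all 18 had a 30-day gap, it rises by 2.3% (0.665).

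**The case against.** The strongest reply is that little of what the study reports depends on this, and most of that reply stands.

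- A reader might infer that every analysis presumes a drug-free start. The protocol does not support that. The week 8 dose-proportionality model, the 25th percentiles and the ROC cut-points contain no starting value. Only the first-order fit and the Css taken from it do.
- A reader might infer a serious bias in the pregnancy effect. At week 8 the shift is about 1% for a plausible handful of women, against an expected 30–58% reduction.
- Very large day-4 ratios can be computed, but the Table 5 footnote gives pregnant women no day-4 blood draw, and at day 4 any residual is divided by a very small expected value.
- PEP still being taken at screening should be caught by the concomitant-drug ban and the medication history in Section 5.1. The zero-gap row is therefore a bound; the real gap is recently completed PEP.
- The randomised cohort is largely protected, because recurrent PEP and related risk factors disqualify. An isolated past course is not named, however.
- The visit 1 sample is drawn pre-dose, and nothing forbids assaying it for TFV-DP.

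What the reply does not remove: no exclusion or washout reaches completed PEP, no rule says to use the entry sample as a check, and the curve cannot absorb a non-zero start.

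**Conclusion.** The point holds as a limited gap in design and analysis. For an affected woman, a 14- to 30-day gap since PEP raises week 1 by 116% to 61% and week 8 by 4% to 2%. It pulls the fitted half-life from 17 days to 6.4–10.0 days and lowers fitted Css by 9–11%. The exposed items are the fitted kinetics, the early concentrations and, slightly, secondary objective 2. The week 8 benchmarks and cut-points are little affected.

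This rests on PEP containing tenofovir, a 28-day course and DBS kinetics. The protocol gives neither the composition of PEP nor the number of recent users, and no PBMC half-life, so nothing here sizes the effect in PBMCs. The fit results also presume that the Section 7.3.1 curve is applied to the pregnant women; Section 7.3.2 does not say which model will be used.

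**What to change.** 1. Assay TFV-DP in the pre-dose DBS (and PBMC) already drawn at visit 1.
2. Record the date and regimen of each woman's last PEP.
3. For any woman with a quantifiable baseline, fit C_t = Css × (1 − e^(−kt)) + C0 × e^(−kt) with the measured C0. In the noise-free case this returns the true Css and the 17-day half-life.
4. Repeat the pregnancy comparison without those women as a sensitivity analysis.
5. State in Section 3.2 how completed PEP is treated, and reconcile this with the exclusion for past PrEP and with recurrent PEP as a qualifying factor.

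The cost is one extra assay per woman (a second if PBMC is included), from blood already collected, and a little analysis work. A long washout is a debatable alternative: 90 days is about 13 weeks, as long as the 13–26 week gestational window itself, so it would exclude many recent users and not merely defer them. Removing women from the main analysis would also be costly in a cohort of 18.
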